3.1.5. Follow-up and End of study

A follow-up visit will occur 3 weeks +/- 7 days after the last study drug administration. At the end of the follow-up period, patients will undergo an EOS visit. This visit occurs 3 weeks after the 8th course of study drug. In the event of premature discontinuation from the study drug or patient withdrawal from the study, an EOS visit is performed within 7 days and prior to administration of any other treatment for CIDP (See Section [8.2.7](#)). The reason for premature study drug discontinuation / study withdrawal should be accurately assessed and entered into the eCRF.

The total duration of the study for a patient is approximately 24 to 29 weeks.

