5.4. Discontinuation criteria / Stopping rule(s)

All patients are free to withdraw from participation in this study at any time, for any reason, and without prejudice. The Investigator must withdraw from the study any patient who requests to stop participating in the study. Patients who withdraw their consent will be asked to undergo the study assessments scheduled at the EOS visit. They will be advised that participation to the EOS visit is voluntary but is their best interest.

The Investigator must discontinue study drug administration to a patient and perform an EOS visit at the request of the Sponsor or if the patient:

- Experiences an AE - including an AE due to a clinically significant laboratory abnormality - that justifies study drug premature discontinuation.

Undergoes protocol deviation that could endanger the patient safety.

- Becomes pregnant.

Moreover, the Investigator may discontinue a patient from study drug administration if:

- Either the patient's adjusted INCAT disability score increases by 1 point, compared to baseline,

AND

Judging on the clinical examination and/or the neurological scales assessments, the Investigator considers change in patient's treatment (such as, administration of another IVIg, increase or initiation of a corticotherapy, immunosuppressive therapy, plasma exchange) is mandatory. Clinical examination findings as well as neurological scales assessments will have to be reported on the EOS visit as appropriate;

- Or the patient's adjusted INCAT disability score increases by at least 2 points compared to baseline.

If a patient is prematurely discontinued, the date and reason of discontinuation will be documented in the eCRF.

If a patient is withdrawn because of an AE, he/she will be followed up until complete resolution or stabilisation of the AE.

Patients lost to follow-up will be considered as discontinued from the study. A patient will be considered as lost to follow-up only after having exhausted all means of contact. Investigators must make every effort to contact the patient and/or his/her family or relatives to obtain the maximum of the per protocol requested information. All contact attempts will be documented in the patient's medical records.

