7.2. Concomitant Medication

The term ‘concomitant medication’ refers to any medication that the patient receives at any time during the study, i.e. from screening to EOS visit. This includes the screening/baseline period,

treatment period and follow-up as defined in the protocol. At each visit, the Investigator will ask the patient about any medication taken since the last visit. All concomitant medication must be recorded in the patient’s medical file and documented on the appropriate pages of the eCRF.

Treatments not allowed during the study are the following:

- Plasma exchange, blood products or derivatives other than the study drug.

- Immunomodulators/immunosuppressors agents (e.g. including but not limited to cyclophosphamide, cyclosporine, interferon- α , interferon- β 1a, anti-CD20, alemtuzumab, aziathioprine, etanercept, mycophenolate mofetil, methotrexate) and haematopoietic stem cell transplantation.
- Introduction or increasing dose of systemic corticosteroids therapy, and/or systemic corticosteroids therapy at a dose higher than 10 mg prednisolone per day, or equivalent. Topical corticosteroids are permitted.
- Loop diuretics administered during the last 24 hours before IVIg infusion planned date. In this case, the study drug infusion date will have to be postponed.

Routine pre-medication (to prevent known drug related adverse reaction) are not recommended to avoid masking potential AEs. However, patients who have routinely been receiving pre-medication with previous Ig treatments may continue to receive the same pre-medication.

Other medications which are necessary for the patient's welfare or well-being may be given at the discretion of the Investigator.

All concomitant medications must be recorded in the patient's medical records and documented on the appropriate pages of the eCRF.

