4.6.2. Secondary efficacy endpoints

The following secondary efficacy endpoints will be studied.

- 1) Responder rate at 12 weeks
Responder rate at 12 weeks will be presented in the same way as for the primary endpoint with exception of the sensitivity analysis using the PPS. Missing assessments at 12 weeks will be imputed using the LOCF approach.
- 2) Time to first response
Time to first response will be analyzed using a Kaplan-Meier (KM) method ([Kaplan 1958](#)). Patients without response will be considered censored at their last assessment of the (adjusted) INCAT disability score. Patients with a non-allowed treatment intake before a first response will be considered censored at the date of the first intake of a forbidden treatment. KM estimates of the mean, median as well as the first and third quartile will be provided together with their associated 95% confidence interval. Reason for censoring will be also indicated. A KM-plot will be provided showing the incidence of a first response over time. Time of censoring will be displayed in the graph. A table will be included below the graph showing the number of patients "at risk" (i.e. without a first response), the number of patients with a first response and the number of censored patients at the time points 0, 6, 12, 18 and 24 weeks. Descriptive statistics will be provided for the time to first response on the subset of patients with response until EOS.
- 3) Percentage of patients at 12 weeks and EOS visit with no change in CIDP treatment
The number and % of patients without change in CIDP treatment will be presented at 12 weeks and at the EOS visit. The associated exact 95% Clopper-Pearson CI will be calculated. A change in CIDP treatment is defined as at least one of the following conditions:

Average dose (g/kg) (see section [5.7.3](#)) of the course is not within 5% of the theoretical study treatment dose (g/kg)

- Theoretical dose is 2 g/kg at the first course and 1 g/kg at subsequent courses for patients with a BMI <30 kg/m²
- Theoretical dose is 1.6 g/kg at the first course and 0.8 g/kg at subsequent courses for patients with a BMI ≥30 kg/m²
- Decrease of the time between courses
 - Time between day 1 of a course and day 1 of the following course is less than 14 days

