- Addition of corticosteroids (equivalent of more than 10 mg/day of prednisone for more than 10 days) or immunosuppressive drugs. As this condition is not possible to derive by programming, the study physician will review all treatments with corticosteroids and immunosuppressive drugs prior to database lock and flag those who fulfil the condition.
- Premature discontinuation of study drug due to insufficient response to IMP and start of another CIDP treatment, corticosteroids, immunosuppressive drugs or plasma exchange

A listing will provide details about the nature of the CIDP treatment changes.

4) Adjusted INCAT disability score

The adjusted INCAT disability score will be presented with descriptive statistics at each visit. The change from baseline in the adjusted INCAT disability score will be analyzed at 12 weeks and EOS visit.

Several graphics will be produced:

- Boxplots over time of a) the at-visit values and b) change from baseline
- Waterfall plots faceted by visit of a) the at-visit values and b) change from baseline

5) Grip strength (kPa) with the Martin vigorimeter in both hands

Actual and normalized (according to the healthy population [Merkies 2000](#)) grip strength will be presented with descriptive statistics at baseline, week 12 and EOS for the dominant hand and the non-dominant hand side by side. The change from baseline in grip strength for the dominant hand and the non-dominant hand will be analyzed at 12 weeks and at the EOS visit. The assessment at screening will be used for the determination of the dominant hand. Normalization according to a healthy population is calculated using the formula (see Section [5.7.5](#)).

6) Rasch-built Overall Disability Scale (R-ODS)

R-ODS will be presented with descriptive statistics at baseline, week 12 and EOS visit. The change from baseline in R-ODS will be analyzed at 12 weeks and at the EOS visit.

7) Medical Research Council (MRC) 12 muscles sum score (0 to 5)

The MRC sum score will be presented with descriptive statistics at baseline, week 12 and EOS visit. The change from baseline in MRC score will be analyzed at 12 weeks and at the EOS visit.

8) Rasch-modified MRC (0 to 3)

The Rasch-modified MRC sum score will be presented with descriptive statistics at baseline, week 12 and EOS visit. The change from baseline in Rasch-modified MRC score will be analyzed at 12 weeks and at the EOS visit.

9) Patient and Investigator Clinical Global Impression (CGI)

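### SAP 4.6.2 item 3 does not count plasma exchange or non-study immunoglobulin added to I10E, or most ways of stopping I10E, as a change in CIDP treatment

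*SAP*

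**What the plan says.** For this endpoint SAP 4.6.2 item 3 states: "The number and % of patients without change in CIDP treatment will be presented at 12 weeks and at the EOS visit", with an exact Clopper-Pearson interval. It continues: "A change in CIDP treatment is defined as at least one of the following conditions". Four conditions follow:

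1. The average course dose is more than 5% away from the theoretical dose.
2. Two courses start fewer than 14 days apart.
3. "Addition of corticosteroids (equivalent of more than 10 mg/day of prednisone for more than 10 days) or immunosuppressive drugs". The study physician reviews corticosteroid and immunosuppressant records before database lock to flag these cases.
4. "Premature discontinuation of study drug due to insufficient response to IMP and start of another CIDP treatment, corticosteroids, immunosuppressive drugs or plasma exchange".

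Protocol 5.4, which allows I10E to be stopped on worsening, gives these examples of a change in the patient's treatment: "administration of another IVIg, increase or initiation of a corticotherapy, immunosuppressive therapy, plasma exchange".

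SAP 4.1 records six reasons for early withdrawal: adverse event, protocol deviation, withdrawal of consent, loss to follow-up, insufficient response, and other. For insufficient-response withdrawals it also tabulates the follow-up treatment.

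**The concern.** The list is closed, so a route that is not on it is not a change. Plasma exchange appears in condition 4, where I10E has been stopped, but not in condition 3, where a treatment is added. Another immunoglobulin product is not in condition 3 either, and the physician review does not cover these two treatments. Leaving I10E altogether for an adverse event triggers nothing, while a course 6% off its theoretical dose does.

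The list also sits awkwardly with the rest of the SAP. Section 3.2 makes a patient withdrawn for lack of efficacy a non-responder on the primary criterion. Under item 3 that same patient is unchanged unless another treatment was started.

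What is at stake is how the reported percentage is read. A reader of the study report will take it as the share of patients who stayed on the planned treatment, yet some who did not will be invisible in it.

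**Working it through.** **Step 1. Test each route against the four conditions.**

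| Route | Caught? |
|---|---|
| Course dose more than 5% off, or interval under 14 days | Yes, conditions 1 and 2 |
| Immunosuppressant added | Yes, condition 3 |
| Corticosteroid added above the dose and duration threshold | Yes, condition 3 |
| Stop for insufficient response, new treatment started | Yes, condition 4 |
| Stop for insufficient response, nothing new started | No |
| Stop for any of the other five recorded reasons | Not through the stop itself |
| Plasma exchange or non-study immunoglobulin while I10E continues | No |

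Of the six recorded reasons, five cannot meet condition 4, and the sixth meets it only together with a new treatment. A stopper in one of the five groups may still be caught by another route, for example by condition 1 if the last course was cut short.

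**Step 2. Ask what happens to a patient who is not caught.** Item 3 does not say.

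- The patient may count as unchanged, because no condition is met.
- The patient may drop out. SAP 3.1 leaves missing observations out of percentages, SAP 3.2 and 4.10.1 confine LOCF to criteria based on the adjusted INCAT score, and the end of SAP 4.6.2 excludes assessments made after a non-allowed treatment. Someone who stops at week 6 has the EOS visit within 7 days and so has no week-12 visit.

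**Step 3. Compare the readings.** The plan gives no expected rate for this endpoint and no discontinuation rate, so there is no plan figure to reproduce, and the number of uncaught patients, k, is an assumption. Let n be the number analysed and c the number of other patients who do have a listed change.

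- Counted as unchanged: (n − c)/n
- Dropped: (n − k − c)/(n − k)
- Counted as changes: (n − k − c)/n

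The first exceeds the third by k/n whatever c is. The second exceeds the third whenever any patient is unchanged, because the numerator is the same and the denominator is smaller.

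Clopper-Pearson limits for x of n are the 2.5% quantile of Beta(x, n − x + 1) and the 97.5% quantile of Beta(x + 1, n − x). When x = n, the lower limit is 0.025^(1/n).

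With n = 42, k = 4, c = 0:

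- Unchanged: 42/42 = 100%, lower limit 0.025^(1/42) = 91.6%
- Dropped: 38/38 = 100%, lower limit 0.025^(1/38) = 90.7%
- Changes: 38/42 = 90.5%, CI 77.4 to 97.3

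Range for k, counting uncaught patients as changes (c = 0), for the planned 42 patients and for a FAS of 38:

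| k | n = 42 | n = 38 |
|---|---|---|
| 2 | 40/42 = 95.2% (83.8 to 99.4) | 36/38 = 94.7% (82.3 to 99.4) |
| 4 | 38/42 = 90.5% (77.4 to 97.3) | 34/38 = 89.5% (75.2 to 97.1) |
| 6 | 36/42 = 85.7% (71.5 to 94.6) | 32/38 = 84.2% (68.7 to 94.0) |

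Each patient is worth 1/42 = 2.4 points or 1/38 = 2.6 points.

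The gap does not depend on starting from 100%. With an assumed c = 10, n = 42 and k = 4, the three readings are 32/42 = 76.2%, 28/38 = 73.7% and 28/42 = 66.7%.

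**The case against.** **The definition already catches most additional treatment.** This stands. A reader might infer that patients who receive additional or replacement treatment are generally reported as unchanged. The documents do not support that: immunosuppressants, corticosteroids above the threshold and switches after insufficient response all count. The gap for added treatment is confined to plasma exchange and non-study immunoglobulin given while I10E continues. Protocol 5.4 lists these as treatments that may prompt stopping I10E, so giving them alongside it would be a deviation. The SAP nevertheless plans for non-allowed treatments during the study, so its definition should cover them.

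**Condition 4 can be derived.** A reader might infer that it can never be met, because after an early stop "an EOS visit is performed within 7 days and prior to administration of any other treatment for CIDP" and because concomitant medication means "any medication that the patient receives at any time during the study, i.e. from screening to EOS visit". That does not follow. The follow-up treatment tabulated under SAP 4.1 supplies what is needed for insufficient-response withdrawals. What remains is that item 3 does not say this field is used, and that SAP 4.1 describes it for those withdrawals only.

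**Nothing says stoppers are counted as successes.** This also stands: the SAP is silent, and some may be censored or missing. Step 2 shows why that does not help, since dropping them raises the percentage as well. The censoring rule also does not reach a patient who stops for an adverse event and takes nothing non-allowed before EOS.

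**Linking discontinuation to insufficient response is a legitimate efficacy-oriented choice.** This stands in part. The documents give the endpoint only a label, not a purpose, and counting loss to follow-up or withdrawn consent as a treatment change mixes attrition and tolerability into the figure. That is an argument for reporting both counts. Early withdrawals are tabulated by reason under SAP 4.1 and treatment changes are listed, so the information is not lost, but it does not appear in the percentage.

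**Conclusion.** The concern holds in limited form. Item 3 leaves out plasma exchange and non-study immunoglobulin given while I10E continues. It also leaves out stopping I10E for any recorded reason other than insufficient response, or for insufficient response with nothing new started. Whether such patients are counted as unchanged or dropped, the reported percentage is higher than if they counted as changes. With an assumed 4 of 42 and no other change, the difference is 100 − 90.5 = 9.5 points.

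The direction follows from the definition. The size does not: it rests on an assumed number of stoppers, none of whom is caught by another condition. The 5% dose rule may well produce other changes, so 100% is a convenient starting point rather than a forecast.

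A reader might also infer that the trial's main result is affected. It is not. This is one descriptive secondary endpoint without a hypothesis test, and the primary test and sample size do not use it. The wording should be settled before database lock.

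**What to change.** In SAP 4.6.2 item 3:

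- Add plasma exchange and any non-study immunoglobulin to the addition condition, and extend the physician review to them.
- State that the follow-up-treatment field of SAP 4.1 is used to derive the discontinuation condition.
- Keep every FAS patient in the denominator at week 12 and at EOS.
- Report, at least as a sensitivity count, the percentage with premature discontinuation for any reason treated as a change, whether or not a new treatment was started, tabulated by reason.

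These changes concern classification in the analysis only and leave clinical management as it is. Discontinuation reasons and on-study treatments are already collected, so no new data are needed. The cost is slightly more analysis work and a slightly less favourable percentage.

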3. GENERAL STATISTICAL CONSIDERATIONS

3.1. Description of Variables

Continuous data will be described using number of valid observations, number of missing observations, mean, standard deviation, median, quartiles, minimum and maximum.

Categorical data will be described using number of missing observations, number of valid observations per category and percentage. Number of missing observations will not be taken into account for the calculation of percentages.

For descriptive statistics, the following number of decimal places (dps) will generally be applied:

- 3 dps for values in [0, 0.9995)
- 2 dps for values in [0.9995, 9.995)
- 1 dp for values in [9.995, 99.95)
- 0 dp for values ≥ 99.95

For negative values the same rule will be followed using the absolute value.

For original case report form (CRF) variables the minimum and maximum will use the same number of dps as the raw data. Statistics on count variables (e.g. number of infusions) will generally be presented with 1 dp while the minimum and maximum will be presented without dp. Percentages will be presented with 1 dp. Exceptions from these rules might be applied when necessary.

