4.6. Efficacy Analyses

The efficacy analyses will be performed on the FAS. The analyses of the primary endpoint will be repeated on the PPS as sensitivity analysis (only if the PPS is different from the FAS). All efficacy endpoints will be analyzed overall and by subgroups of relapsing Ig-pretreated patients and Ig-naïve patients. Endpoints will also be listed by patient status (Ig-naïve/Ig-pretreated).

If a patient is treated with a non-allowed treatment during the study period, then all efficacy variables measured after the intake of these non-allowed treatments will be censored for the efficacy analyses. Assessments of primary and secondary criteria after a forbidden treatment will be flagged in all listings.

The following treatments are not allowed during the study:

- Any other investigational product administered within the last month prior to screening
- Plasma exchange, blood products or derivatives other than the study drug.
- Immunomodulatory or immunosuppressant agents (e.g. including but not limited to cyclophosphamide, cyclosporine, interferon- α , interferon- β 1a, anti-CD20, alemtuzumab, aziathioprine, etanercept, mycophenolate mofetil, methotrexate) and hemotopoeitic stem cell transplantation.
- Oral or systemic corticosteroids therapy if administered with an increasing dosage or introduced at a dose higher than 10 mg daily prednisolone or equivalent. Topical corticosteroids are allowed.

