The CGI-S (*Severity of illness*) assessment by patients and investigators will be presented side by side with descriptive statistics at the visits baseline, week 12 and EOS for the categories *Normal*,

not at all ill / Borderline ill / Mildly ill / Moderately ill / Markedly ill / Severely ill / Among the most extremely ill patients (only for the investigator judgment). A shift table will be provided for the change from baseline at week 12 and EOS.

The CGI-I (*Improvement*) assessment by patients and investigators will be presented side by side with descriptive statistics at the visits week 12 and EOS for the categories *Very much improved / Much improved / Minimally improved / No change / Minimally worse / Much worse / Very much worse*.

The CGI-E (*Efficacy index*) assessment by patients and investigators will be presented with descriptive statistics at the visits week 12 and EOS in a 4×4 cross-table crossing Therapeutic effect categories (*Marked / Moderate / Minimal / Unchanged or Worse*) with Side effect categories (*None / Do not significantly interfere with patient's functioning / Significantly interferes with patient's functioning / Outweighs therapeutic effect*). The sum over the number and % of patients shown the 4×4 cross-table (16 cells) will correspond to the number of patients with valid assessments and 100% respectively. The cross-table will also show a row and column with the Total for each dimension corresponding to the separate description of the Therapeutic effect and the Side effects.

For the endpoints 4) to 8) the one sample Hodges-Lehmann estimator ([Hodges 1963](#) and [Han 2008](#)) and the associated 95% confidence interval will be calculated for all at-visit values, as well as for the change from baseline to 12 weeks and EOS visit for both the overall and patient subgroups. The change from baseline for the endpoints 4) to 8) will be tested using a one sample Wilcoxon signed-rank test, for the overall set of patient only. All statistical tests will be descriptive and will use a two-sided significance level of $\alpha=5\%$.

Statistical tests will not be performed by subgroup.

For all secondary efficacy endpoints, assessments performed after the use of a non-allowed treatment will be censored (not used in the statistical summaries).

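### The censoring rule for non-allowed treatments does not exempt the 'no change in CIDP treatment' endpoint and conflicts with that endpoint's own definition

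*SAP*

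**What the plan says.** Three places in the SAP set the censoring rule. Section 3.5.1 (Populations) and section 4.6 (Efficacy Analyses) both say that, once a patient takes a non-allowed treatment, "all efficacy variables measured after the intake of these non-allowed treatments will be censored for the efficacy analyses". The last sentence of 4.6.2 repeats it for the secondary endpoints: "For all secondary efficacy endpoints, assessments performed after the use of a non-allowed treatment will be censored (not used in the statistical summaries". None of the three makes an exception.

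Item 3 of 4.6.2 is one of those secondary endpoints. It is the percentage of patients whose CIDP treatment has not changed at week 12 and at EOS, with an exact Clopper-Pearson 95% CI. On its definition the SAP says "A change in CIDP treatment is defined as at least one of the following conditions". One of the conditions is "Addition of corticosteroids (equivalent of more than 10 mg/day of prednisone for more than 10 days) or immunosuppressive drugs". Because this condition cannot be programmed, "the study physician will review all treatments with corticosteroids and immunosuppressive drugs prior to database lock and flag those who fulfil the condition". A listing describes the changes.

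The non-allowed list in SAP 4.6 includes "Oral or systemic corticosteroids therapy if administered with an increasing dosage or introduced at a dose higher than 10 mg daily prednisolone or equivalent" and "Immunomodulatory or immunosuppressant agents (e.g. including but not limited to cyclophosphamide" among others.

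On denominators, SAP 3.1 states: "Number of missing observations will not be taken into account for the calculation of percentages". SAP 4.10.1 limits LOCF to criteria based on the adjusted INCAT score, so LOCF does not apply to item 3.

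**The concern.** Any corticosteroid addition that meets the item 3 threshold is also a non-allowed treatment, and so is any added immunosuppressant. The drug that makes a patient changed under item 3 is therefore the same drug that triggers censoring of that patient's later efficacy data. A patient who starts one at week 8 while continuing I10E has both the week-12 and the EOS status falling after intake. If that status is treated as unusable, SAP 3.1 takes the patient out of the numerator and the denominator, and no imputation puts the patient back.

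Item 3 is meant to show how many patients were managed on I10E without other CIDP therapy. If the patients who needed added therapy are left out, the percentage and its confidence limits describe only the remainder. The text lets two competent programmers reach different percentages, and the literal route usually gives the more favourable one.

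**Working it through.** **Plan's own figure.** The SAP gives no expected value for item 3. Its only design figure is 38 evaluable patients (SAP 2.3), used here as the base. That figure reproduces: with n = 38 and success at 19 or more responders, the exact one-sided alpha is 0.0244 at 33.3% and power is 0.9216 at 60%. With n = 37, power is 0.8920, so 38 is the smallest n that reaches 90%.

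**How the SAP treats each endpoint after a non-allowed treatment.**

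| Endpoint | Tailored instruction |
|---|---|
| Primary response (4.6.1) | Last score before intake replaces the EOS score |
| Item 1, response at week 12 | Missing values filled by LOCF |
| Item 2, time to first response | Kaplan-Meier censoring at the date of intake |
| Item 3, no change in CIDP treatment | None; only the general rule and item 3's own definition |

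**Inputs for the illustration.** N = 38 (SAP 2.3). k = patients who add a qualifying drug before the time point while staying on study drug. o = patients with another item 3 change, such as dose or interval. Neither k nor o is in the documents; both are assumed.

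- Counted as changed: (N − o − k) / N
- Censored and dropped: (N − o − k) / (N − k)
- Difference: k(N − o − k) / [N(N − k)], which is k/N when o = 0

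| o | k | Counted (95% CI) | Censored (95% CI) | Difference, points |
|---|---|---|---|---|
| 0 | 1 | 37/38 = 97.4% (86.2–99.9) | 37/37 = 100% (90.5–100) | 2.6 |
| 0 | 2 | 36/38 = 94.7% (82.3–99.4) | 36/36 = 100% (90.3–100) | 5.3 |
| 0 | 4 | 34/38 = 89.5% (75.2–97.1) | 34/34 = 100% (89.7–100) | 10.5 |
| 0 | 6 | 32/38 = 84.2% (68.7–94.0) | 32/32 = 100% (89.1–100) | 15.8 |
| 0 | 8 | 30/38 = 78.9% (62.7–90.4) | 30/30 = 100% (88.4–100) | 21.1 |
| 3 | 4 | 31/38 = 81.6% (65.7–92.3) | 31/34 = 91.2% (76.3–98.1) | 9.6 |

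**The opposite direction.** SAP 4.6 sets no minimum duration for a corticosteroid introduced above 10 mg/day, whereas item 3 requires more than 10 days. A shorter course is therefore non-allowed without being a change. The same holds for a blood product given without stopping study drug. Let s be the number of such patients, otherwise unchanged. With N = 38, o = 3, k = 0 and s = 4, keeping them gives 35/38 = 92.1% and dropping them gives 31/34 = 91.2%, which is 0.9 points lower (o·s / [N(N − s)] = 12/1292). With o = 0 both results are 100%.

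**Who is exposed.** Protocol 3.1.5 and 8.2.7 place the EOS visit before any other CIDP treatment when study drug is stopped early. Those patients' EOS status is not measured after a non-allowed treatment. The exposed patients are those who add a drug and stay on I10E. Protocol 7.2 prohibits this, but Protocol 5.4 says that the investigator may, not must, stop study drug for worsening. Item 3 also lists drug addition separately from discontinuation, so the SAP foresees such patients.

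**The case against.** The strongest reply is that item 3 already answers the question. A specific definition normally prevails over a general closing sentence, and this one makes the addition a change, has a physician flag it and lists it. If flagged patients were then deleted, the flag would have almost no purpose. The rule also censors assessments made after intake, whereas the item 3 event is the intake itself, read from medication records. A patient with a known, flagged change is not obviously a missing observation. Protocol 12.9.2.2, on the secondary endpoints, censors only adjusted INCAT scores.

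Much of this stands. A reader might infer that the SAP does remove these patients and that the percentage is therefore driven to 100%. The documents do not support that. Nowhere does the SAP say that they leave item 3, and counting them is probably what the sponsor intends. A result of 100% needs no dose or interval change in any remaining patient, and short courses pull the other way.

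The reply does not settle the matter, however. The primary endpoint and items 1 and 2 have tailored handling and item 3 has none, so the general rule is the only censoring instruction that reaches it. Being flagged and listed does not put a patient in the percentage, because SAP 5.1 keeps data recorded after a non-allowed treatment in the listings anyway. Protocol 12.9.1.1 censors all efficacy variables, so the protocol points both ways.

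**Conclusion.** The concern holds as an unresolved conflict between a general censoring rule and item 3's own definition. Removal of these patients is a possible literal outcome, not a settled one.

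If the rule is applied literally, the no-change percentage rises by k/38 when there are no other changes: 5.3, 10.5 or 15.8 points for 2, 4 or 6 additions. With 3 other changes and 4 additions the rise is 9.6 points. Non-allowed treatments that are not item 3 changes can lower the percentage instead, by 0.9 points in the case worked. These sizes rest on assumed counts, 38 patients in the FAS and additions made before the time point by patients who continue I10E.

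The consequence is confined to a descriptive secondary endpoint that has a confidence interval but no test (SAP 3.4 and 4.6.2). The primary analysis and the sample size are unaffected. It should still be corrected before the analysis, because the choice affects a reported percentage and its interval and is otherwise left to the programmer.

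**What to change.** Add to SAP 4.6 and 4.6.2:

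> The censoring rule for non-allowed treatments does not apply to item 3. A patient who meets any item 3 condition is counted as changed at that time point and all later ones; a patient whose non-allowed treatment does not meet an item 3 condition stays in the analysis as not changed. The denominator is the full FAS.

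Because this fixes the denominator, the SAP should also say how item 3 classes a patient who leaves before a time point without meeting any condition; it does not say so now.

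The cost is a few lines in the SAP and no new data, since the physician's review is already planned. The downside for the sponsor is that the reported percentage may be less favourable.
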